# 9.3 Cytokines

If grant support is available, serum cytokine profiling will be performed using the Quanterix Simoa platform evaluating systemic IL-12p70 as well as 35 additional cytokines including IFN-gamma, TNF-alpha, IL-1β, IL-2, IL-4, IL-5, IL-6, IL-8, IL-10, IL-17A and TGF-beta.

### 9.4 T cell response

SARS-CoV-2 (S) protein-specific cellular immune responses will be measured by cytokine-release assay for type I, type 2 and IL-17 cytokine responses using cytokine bead arrays. IFN-gamma positive responses will be assessed by interferon-gamma ELISA and either intracellular cytokine staining (ICS) or ELISPOT assay using unfractionated PBMC and peptide pools of epitopes considered to be dominant epitopes for the HLA expressed by the specific subject. If predicted HLA-binding epitopes fail to identify targets of immune response, peptide pools containing 15-mer peptides overlapping by 11 amino acids will be explored. Our prediction is that the cytokine response to whole protein will be dominated by CD4+ T-cell response and that the response to overlapping peptides will comprise both CD4+ and CD8+ T-cell responses.

### 9.5 B cell response

Analysis of antibody responses to SARS-CoV-2 spike (S) glycoprotein will be performed using Microaffinity proteomic (MAP) bead technology or ELISA. Bead arrays containing SARS-CoV-2 proteins will be used to assess IgM and the isotype of IgG responses that develop following vaccination. Humoral response will also be monitored by B-Cell ELISPOT evaluating PBMC for IgA, IgM, and IgG response to the COVID-19 S spike to determine the B cell response that has developed.

### 9.6 Coordinated humoral/cellular response

Grant support is being requested to perform single-cell RNA sequencing at day 0, 15, 30, 45, 60 and 90. It is planned that paired αβ TCRseq and tandem BCRseq using the Archer Immunoverse platform will allow tracking of T and B cell clones and provide opportunities to assess whether dominant clones recognize epitopes of the SARS-CoV-2 spike protein. We have successfully used this technology to isolate tumor-reactive TCRs from peripheral blood of subjects on a cancer vaccine trial. We postulate that persisting neutralizing Ab responses will result from a coordinated CD4, CD8 and B cell response to the SARS-CoV-2 spike (S) glycoprotein.

#### 9.7 Whole genome sequencing

Whole genome sequencing will be performed to assess polymorphisms in immune-response related genes. It will also provide the HLA haplotypes. This information will be evaluated for relationships to the magnitude of the immune response to vaccination. The studies performed here, while only a small number of subjects and some of which are exploratory in nature, may provide insights into the apparently unique biology of this virus. We will also look for correlations with the depth and magnitude of response to vaccination.

# 9.8 Clinical Outcomes and Surveillance Database

A coded, de-identified clinical database will be maintained by the study PI or clinical research as delegated by the study PI. The database and codes key will be housed on a password and encryption protected network drive, only accessible to the study PI and delegated staff. Participants will provide consent for inclusion in the longitudinal study database at enrollment. Clinical data will be collected from time of enrollment to a minimum of five years clinical surveillance post completion of treatment, or death or loss to follow-up. Such data will include but not be limited to: age at time of study, medications, medical and surgical history.

# 10. REGULATORY & REPORTING REQUIREMENTS

#### 10.1 Common Terminology Criteria for Adverse Events (CTCAE)

This study will utilize the Common Terminology Criteria for Adverse Events (CTCAE) active version. The CTCAE active version can be accessed from the CTEP home page (http://ctep.cancer.gov).

#### 10.2 Definitions

Serious adverse event: A serious adverse drug or device experience is defined as any adverse drug or device experience occurring at any dose or experience with the device that results in any of the following outcomes: Death, a life-threatening adverse drug or device experience, hospitalization or prolongation of existing hospitalization, a persistent or significant disability/incapacity, or a congenital anomaly/birth defect. Important medical events that may not result in death, be life-threatening, or require hospitalization may be considered a serious adverse drug or device experience when, based upon appropriate medical judgment, they may jeopardize the participant or subject and may require medical or surgical intervention to prevent one of the outcomes listed in this definition.

### Unexpected adverse event:

Any adverse drug or device experience, the specificity or severity of which is not consistent with the current investigator brochure; or, if an investigator brochure is not required or available, the specificity or severity of which is not consistent with the risk information described in the general investigational plan or elsewhere in the current application, as amended.

Associated with the use of the drug / device / intervention: There is a reasonable possibility that the experience may have been caused by the drug or device.

Disability:

A substantial disruption of a person's ability to conduct normal life functions.

#### Life-threatening adverse event:

Any adverse drug or device experience that places the participant or subject, in the view of the investigator, at immediate risk of death from the reaction as it occurred, i.e., it does not include a reaction that, had it occurred in a more severe form, might have caused death.

### Unanticipated Problem

An unanticipated problem is an adverse event that is (i) unexpected; (ii) serious; and (iii) felt by the investigator to be possibly, probably, or definitely related to the research intervention. Only adverse events that meet this definition need be reported to the IRB.

For more information on the definition of an unanticipated problem and reporting requirement, consult the current PH&S AE Guidelines published on the IRB website (http://phsnet.phsor.org/institutional\_review\_board).

# 10.3 Adverse Event Reporting

#### PSJH IRB

An unanticipated event that is serious and definitely or probably caused by the study treatment (drugs or device) will be reported to the IRB in accordance with their guidelines and within their timelines.

#### FDA Reporting

The Principal Investigator is responsible for determining whether or not the suspected adverse reaction meets the criteria for expedited reporting in accordance with Federal Regulations (21 CFR §312.32). A suspected adverse reaction must be both serious and unexpected in order to meet the reporting requirements.

An adverse event or suspected adverse reaction is considered "unexpected" if it is not listed in the investigator brochure, the device user manual, or is not listed at the specificity or severity that has been observed; or, if an investigator brochure or device user manual is not required or available, is not consistent with the risk information described in the general investigational plan or elsewhere in the current application, as amended.

An adverse event or suspected adverse reaction is considered "serious" if, in the view of either the investigator, it results in any of the following outcomes: Death, a life-threatening adverse event, hospitalization or prolongation of existing hospitalization, a persistent or significant incapacity or substantial disruption of the ability to conduct normal life functions, or a congenital anomaly/birth defect. Important medical events that may not result in death, be life-threatening, or require hospitalization may be considered serious when, based upon appropriate medical judgment, they may jeopardize the participant or subject and may require medical or surgical intervention to prevent one of the outcomes listed in this definition.

The timeline for submitting an IND safety report to FDA is no later than 15 calendar days after the Investigator determines that the suspected adverse reaction qualifies for reporting (21 CFR 312.32(c)(1)).

Any unexpected fatal or life-threatening suspected adverse reaction will be reported to FDA no later than 7 calendar days after the Investigator's initial receipt of the information (21 CFR 312.32(c)(2)).

Any relevant additional information that pertains to a previously submitted IND safety report will be submitted to FDA as a Follow-up IND Safety Report without delay, as soon as the information is available (21 CFR 312.32(d)(2)).

Any potentially vaccine-related immune-mediated medical condition (see Appendix 2) that occurs will be considered unexpected. Expedited reporting requirements (as outlined in 21 CFR 312.32) will be followed for any adverse event assessed as a serious and unexpected suspected adverse reaction (SUSAR).

### **10.4 Continuing Review and Final Reports**

An annual progress report (continuing review) will be submitted to the IRB for the duration of the study. A final report to the IRB will be submitted at the summation of the study.

All IND annual reports, clinical trial reports, and clinical trial report addenda submitted to the FDA will include tabulated summaries of available adverse event data for potentially immune-mediated medical conditions reported during the trial, categorized by MedDRA term. These summaries will include any conditions reported during the trial that match the terms listed in Appendix 2, as well as any other potentially immune-mediated medical conditions (pIMMCs) reported during the trial that do not appear on the list in Appendix 2. For each adverse event included in the summaries, a case narrative will be provided, along with an assessment of the seriousness of the event and causal relationship to study vaccine, as required by 21 CFR 312.32.

Collection of MAAE data beyond 6 months after the last study vaccination will not delay submission of clinical trial reports and initiation of subsequent clinical trials, and final analyses of MAAEs may be submitted in clinical trial report addenda.

The safety analysis in the final clinical study report will include the number and proportion of subjects in each cohort reporting 1) each solicited AE of any grade through seven days following any dose and each dose, 2) each solicited AE grade 3 and greater within seven days following any dose and each dose, 3) unsolicited AEs of any grade reported at a minimum through 28 days following dose 2, 4) unsolicited AEs grade 3 and greater reported at a minimum through 28 days following dose 2, 6) SAEs, MAAEs, and pIMMCs reported through one year following dose 2. In addition, it will include the number and proportion of subjects in each cohort of each category of AE that the investigator assessed as related.

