#### Outcome Measures

[figure not shown]
- Toxicity and Adverse Events (AEs) based on FDA Guidance for Industry 2005D-0155: Toxicity Grading Scale for Healthy Adult and Adolescent Volunteers Enrolled in Preventive Vaccine Clinical Trials.
- 90 day monitoring of hematology, serum chemistry, and creatine phosphokinase.
- 90 day monitoring of serial physical exam, vital signs, and durable pain score.
- Extended monitoring of Medically Attended Adverse Events (MAAEs) for potentially immune-mediated conditions (pIMMCs)

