# 6.5 Subject Discontinuation & Replacement

In the event of a positive COVID-19 qPCR test result during the interval between 1st and 2nd vaccination, subject will discontinue study treatment and may be replaced. In the event of treatment delay exceeding 21 days, and absent DLT, subject will discontinue study treatment and may be replaced. In the event of a confirmed positive serum or urine pregnancy test, between 1st and 2nd vaccination, subject will discontinue study treatment and may be replaced. And otherwise, subjects who enroll in the study, and do not complete study treatment for reasons other than DLT, may be replaced.

Discontinuation for the following reasons does not allow for subject replacement: an SAE assessed as definitely/probably related to the investigational product; any Grade 3 or higher unsolicited AE, assessed as definitely/probably related to the investigational product; a new medical condition that would qualify for study exclusion; suspicion or diagnosis of pIMMC, as per section 6.1.

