- 7. Adverse events/toxicity daily query by use of diary or RN/CRC phone call for seven days following each vaccination, including but not limited to injection site pain, redness, swelling, fatigue, headache, nausea, vomiting, diarrhea, myalgia, arthralgia, rash, new pain, dyspnea and temperature (see Appendix 1: Toxicity Grading). Subjects utilizing the diary for AE collection will be called on Day 7 by RN/CRC to review diary entries. On days 1, 15, 30, 45 where vital signs are indicated, AE assessment should be conducted in person by RN, or other PI designee.
- 8. Monitor for MAAEs at months 1, 2, 3, 6, 12 and 18 with contact by research RN or research associate for potentially immunemediated medical conditions (see Appendix 2: MAAEs/pIMMCs); repeat COVID-19 qPCR and antibody testing to be performed at any time during the 18 months safety monitoring in the event of potential exposure to SARS-CoV-2 (i.e., close contact tests positive for SARSCoV-2) or symptoms of SARS-CoV-2 infection, with full immunodynamic profiling (section 9) to be performed at the same time. In addition, voluntary extended immune monitoring under longitudinal research specimen protocol, will be offered to all study subjects at day 90.
- 9. Concomitant medications (including those administered prophylactically) will be collected from 30 days prior to Day 1 through Day 90. In addition, all medications associated with SAEs, MAAEs (including pIMMCs) will be collected through 18 months.

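### The dose 2 unsolicited-AE summary must reach at least Day 58, but the last scheduled general AE assessment is Day 45, so events with no other route in are captured only if volunteered

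*Combined protocol and SAP*

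**What the plan says.** Section 10.4 lists what the final safety analysis will report by cohort. Two items concern unsolicited events: "unsolicited AEs of any grade reported at a minimum through 28 days following dose 2" and "unsolicited AEs grade 3 and greater reported at a minimum through 28 days following dose 2".

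The general AE schedule is in section 7, footnote 7. It sets a "daily query by use of diary or RN/CRC phone call for seven days following each vaccination", and then: "On days 1, 15, 30, 45 where vital signs are indicated, AE assessment should be conducted in person by RN" or another designee.

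In the calendar's AE row, Days 60 and 90 are marked for medically attended AEs (MAAEs). Footnote 8 describes these as monitoring "with contact by research RN or research associate for potentially immunemediated medical conditions" (pIMMCs), and the primary outcome measures in section 3 make the same link. Footnote 9 suggests a wider sense of MAAE, since "all medications associated with SAEs, MAAEs (including pIMMCs) will be collected through 18 months", but even then the event must be medically attended.

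Day 60 is a real visit. Chemistry, CPK, blood count, urinalysis, COVID-19 testing and concomitant medications are all scheduled. Day 90 adds a physical examination.

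**The concern.** Safety is the only primary objective, and section 11.1 summarises it as the percentage of participants with AEs. A proportion labelled as covering 28 days after dose 2 invites the reader to assume that participants were asked about the whole period. If the calendar is followed as written, general questioning stops about halfway through, and the remainder depends partly on what participants choose to mention.

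The events at risk are not all trivial. In Appendix 1, Grade 3 fatigue and Grade 3 myalgia are defined by preventing daily activity, with no medical visit required. The schedule is also uneven: the prime is followed by general AE assessments across a full 28 days and the boost is not. A comparison of post-prime and post-boost unsolicited AEs would therefore partly reflect how often people were asked.

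**Working it through.** The plan states no coverage figure to reproduce. Day 58 follows from its own dates.

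**Inputs**
- Dose 1 on Day 1; dose 2 on Day 30, window ±1 day (section 7).
- General AE assessments on Days 1, 15, 30 and 45; window ±1 day on Days 15, 30 and 45 (section 7 and footnote 7).
- Daily query for 7 days after each dose (footnote 7).
- Reporting period of at least 28 days after dose 2 (section 10.4).
- Day 60 visit, window ±2 days (section 7).
- 9 participants per cohort, 36 in all (section 11.1).

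**1. After the prime.** General assessments fall at 15 − 1 = +14 days and 30 − 1 = +29 days, so 28 days are covered.

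**2. After the boost, on time.** The period ends on Day 30 + 28 = Day 58. The daily query ends at +7 days. The last general assessment is at 45 − 30 = +15 days. Days after it: 58 − 45 = 13, and 13/28 = 46%.

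**3. Visit windows.** Gap = (dose 2 day + 28) − (day of the Day 45 visit).
- Smallest: 29 + 28 − 46 = 11 days (39%).
- Largest: 31 + 28 − 44 = 15 days (54%).

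These are shares of days, not of events.

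**4. What reaches the record for onsets in Days 46 to 58**

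| Type of event | Scheduled route |
|---|---|
| Immune-mediated, or medically attended on the wider reading of MAAE | MAAE contact at Day 60 |
| Laboratory abnormality still present | Day 60 blood and urine tests |
| Event needing a medication | Concomitant medications, collected through Day 90 |
| Anything else | None; volunteered only |

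The weekly AE review in section 10.7 is carried out by study staff and specifies no participant contact, so it does not fill the last row.

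**5. Would a query at Day 60 close the gap?** On time, yes: Day 60 is 2 days past Day 58. Over the windows the visit falls on Days 58 to 62 and the period ends on Days 57 to 59. The one shortfall is a boost on Day 31 with the visit on Day 58: 58 − 31 = +27 days, one day short. The query therefore needs a floor of 28 days after the actual dose 2 date.

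**6. Sensitivity of the table.** One participant whose only AE is missed moves a cohort percentage by 1/9 = 11 points, or the overall percentage by 1/36 = 2.8 points. The documents give no unsolicited-AE rate, so no expected number of missed participants can be derived.

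**The case against.** The best defence is that the calendar is ambiguous and does not show a definite gap. The Day 30 cell also reads MAAEs, yet footnote 7 requires a general AE assessment that day, so an MAAE entry does not by itself exclude one. Footnote 7's list of days can be read as saying where assessment must be in person, without saying that collection stops elsewhere. Section 10.9 says that study-specific case report forms, completed after each visit, document safety. Those forms are not in the documents, and an open AE field at Day 60 cannot be ruled out. Finally, this is a small descriptive trial, and the more serious events mostly have another route.

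Part of this stands. The routes in the table above are real, and the Grade 3 and above row is less exposed because several Grade 3 definitions involve narcotics, intravenous fluids, medical care or laboratory values. But what brings Day 30 in is that footnote 7 names it. Day 60 is not named, and no other section schedules a general AE query after Day 45. A reporting commitment should not depend on a form field that the protocol does not call for.

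A reader might also infer more than the documents support:

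- *That nothing is asked about Days 46 to 58.* The Day 60 contact, laboratory tests and medication review contradict this.
- *That a delayed boost leaves 21 of 28 days (75%) uncovered.* Section 6.5 says: "In the event of treatment delay exceeding 21 days, and absent DLT, subject will discontinue study treatment and may be replaced". A boost on Day 30 + 21 = Day 51 would put the end of the period at Day 79 and the end of the daily query at Day 58, and 79 − 58 = 21. This needs visits to stay fixed to Day 1. Days 31 and 32 plainly mirror Days 2 and 3 as post-dose visits, so that reading is unlikely. What remains is that the protocol never says later visits move with the boost.
- *That lasting skin changes at the boost site are missing from the table.* Section 6.1 notes that such changes can still be seen at about four weeks. Section 10.4, however, promises numbers of participants with events and not duration; occurrence is covered by the 7-day query and Day 45.

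**Conclusion.** The point holds for a defined residue of events. For an on-time boost, 13 of the 28 days promised in section 10.4 (11 to 15 over the ±1 day windows) lie after the last scheduled general AE assessment. In those days, AEs that are not medically attended or immune-mediated, need no medication and show no laboratory abnormality are captured only if volunteered. The dose 2 unsolicited-AE proportions may therefore be too low, more plausibly in the any-grade row than in the Grade 3 and above row.

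This assumes that the calendar is followed as written and that no unseen form adds a general AE question at Day 60. The size is a count of days; the number of events affected is unknown. The point goes beyond missing detail, because following the protocol exactly yields a primary-safety summary with weaker ascertainment than its label implies. It does not suggest that serious or immune-mediated events would go undetected.

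**What to change.** In the section 7 calendar and footnote 7:

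1. Add a general AE query at the existing Day 60 visit, with recall since the Day 45 assessment.
2. Require that query to take place at least 28 days after the actual dose 2 date.
3. State that post-boost visits are timed from the actual dose 2 date.

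A brief look at the injection site at the same visit is optional and is not needed for the section 10.4 table.

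The cost is a few minutes and a few case report form fields at a visit already held. When the boost is delayed, later visits move back by the length of the delay, up to the 21 days allowed. No new visit is needed, and dosing, the stopping rules, Appendix 1 and the section 10.4 tables are unchanged.

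### Safety contacts run to month 18, but the listed analysis of SAEs, MAAEs and pIMMCs stops one year after dose 2, and no scheduled query is stated for SAEs or non-immune MAAEs after Day 90

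*Combined protocol and SAP*

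**What the plan says.** **Follow-up.** Footnote 8 of the study calendar (section 7) reads: "Monitor for MAAEs at months 1, 2, 3, 6, 12 and 18 with contact by research RN or research associate". It goes on to give the subject of the contact: "for potentially immunemediated medical conditions (see Appendix 2: MAAEs/pIMMCs"). The same footnote provides for repeat SARS-CoV-2 testing "at any time during the 18 months safety monitoring in the event of potential exposure to SARS-CoV-2" or symptoms. Footnote 9 adds that "all medications associated with SAEs, MAAEs (including pIMMCs) will be collected through 18 months".

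**Outcome measure.** The fourth measure under the primary objective (section 3) is "Extended monitoring of Medically Attended Adverse Events (MAAEs) for potentially immune-mediated conditions (pIMMCs").

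**Analysis.** Section 10.4 lists what the safety analysis in the final report will contain, as numbers and proportions by cohort. The last item, numbered 6, is "SAEs, MAAEs, and pIMMCs reported through one year following dose 2". The same section makes two further provisions. Collecting MAAEs beyond 6 months after the last vaccination is not to hold up reports, and "final analyses of MAAEs may be submitted in clinical trial report addenda". In addition, every IND annual report, study report and addendum sent to the FDA must tabulate the pIMMCs that came to light in the course of the trial, each event with a narrative and an assessment of seriousness and causality. That tabulation has no one-year limit.

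**The concern.** Two things do not line up.

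First, the time horizon. The protocol schedules safety contacts to month 18, but its only listed count of long-term events ends about five months sooner. Items 3 and 4 of the same list are worded as a floor (at least 28 days after dose 2). Item 6 is not, so it reads as a cut-off.

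Second, ascertainment. Item 6 promises proportions for three separate categories. From month 6 onwards the only scheduled contact is described by one of them, the pIMMCs. A table built this way could show few or no late SAEs or non-immune MAAEs because no scheduled question is stated that would bring them out. The protocol has its own reasons to want these events. Section 2 discusses antibody-dependent enhancement, and COVID-19 is not among the conditions in Appendix 2. A hospitalisation for COVID-19 at month 15 could be recorded as an SAE, yet no planned count would include it.

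**Working it through.** There is no stated power, alpha or effect size behind this point, so the check is calendar arithmetic followed by a comparison of the text.

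**Inputs**
- Contacts at months 1, 2, 3, 6, 12 and 18 (section 7, footnote 8).
- Anchor: the calendar puts MAAE monitoring at Days 30, 60 and 90, which correspond to months 1, 2 and 3. Months are therefore counted from Day 1. This is inferred, because the protocol does not state it.
- Dose 2 on Day 30, window ±1 day (section 7), with a delay of up to 21 days before treatment is discontinued (section 6.5). Dose 2 can thus fall from Day 29 to Day 31 + 21 = 52.
- Analysis horizon: one year after dose 2 (section 10.4).

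**Formulas**
- Cut-off day = dose-2 day + 365.
- Follow-up outside the analysis = month-18 day − cut-off day.
- Month-18 day = 18 × 30.44 = 548 with calendar months, or 18 × 30 = 540 with 30-day months.

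| Dose-2 day | Cut-off day | Days outside, calendar months | Days outside, 30-day months |
|---|---|---|---|
| 29 | 394 | 548 − 394 = 154 (28%) | 540 − 394 = 146 (27%) |
| 30 | 395 | 548 − 395 = 153 (28%) | 540 − 395 = 145 (27%) |
| 52 | 417 | 548 − 417 = 131 (24%) | 540 − 417 = 123 (23%) |

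Percentages are of the 18 months. For dose 2 on Day 30, the cut-off is month 395 / 30.44 = 13.0. Across the whole range, 123 to 154 days (about 4 to 5 months) lie outside the listed analysis. If months were instead counted from dose 2, the month-12 contact would coincide with the cut-off and the last 6 months would lie outside.

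**What the plan provides for each category**

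| Category | Stated subject of contacts after Day 90 | Counted to one year after dose 2 | After one year |
|---|---|---|---|
| pIMMCs | Yes | Yes | Tabulated with narratives in reports and addenda |
| Non-immune MAAEs | Not stated | Yes | Final MAAE analyses may go in addenda; content and horizon not given |
| SAEs | Not stated | Yes | No planned analysis |

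No other section fills the empty cells. Section 11.1 promises percentages of participants with adverse events but gives no time window. Section 9.8 sets up a database with at least five years of clinical surveillance, including medications and medical and surgical history, but gives no contact schedule, event query or link to the safety analysis. Footnote 9 implies that SAEs, and MAAEs wider than pIMMCs, are expected to be known to month 18, without saying how they are elicited.

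**The case against.** The strongest reply is that the protocol protects what matters and that the gap is partly deliberate. The fourth outcome measure concerns immune-mediated conditions, and section 10.4 requires those reported during the trial to be tabulated with narratives and without a one-year limit. The provision that late MAAE collection must not delay reports shows that a staged analysis was intended. The permissive verb can be read as governing where the final MAAE analysis appears, not whether it is done. All of this stands, and it rules out several stronger readings.

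- *A reader might infer that months 13 to 18 are thrown away, or that a primary outcome measure is lost.* The pIMMC tabulation contradicts this. What is missing after one year is a listed count and proportion by cohort, and any analysis of SAEs.
- *A reader might infer that the contacts are the sole source of long-term safety information.* Section 9.8 provides five-year surveillance, and the halting rule for related deaths and SAEs (section 6.3) and expedited reporting (section 10.3) have no stated end date.
- *A reader might infer that callers will elicit Appendix 2 conditions and nothing else.* Footnote 8 also covers COVID-19 exposure and symptoms, footnote 9 presupposes wider capture, and section 10.4 expects pIMMCs that are not on the list. The query is unspecified; other events are not excluded.
- *A reader might infer that events between the month-12 contact and the cut-off rest on recall at month 18.* Nothing says so, and case histories under section 10.6 include medical records and hospital charts.
- *A reader might infer a measurable loss of precision from the shorter horizon.* Section 10.4 specifies proportions, not rates. With no events, the one-sided 95% upper bound is 1 − 0.05^(1/36) = 8.0% overall and 1 − 0.05^(1/9) = 28% for a cohort of nine, whichever horizon is used.

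The objection does not supply a planned count of late SAEs. Nor does it supply a stated question behind the SAE and non-immune MAAE proportions.

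**Conclusion.** The inconsistency is real but modest. Item 6 of section 10.4 ends at about Day 395, while scheduled contacts end at about Day 548. That leaves 123 to 154 days outside the listed number-and-proportion analysis, assuming months run from Day 1 and dose 2 falls between Days 29 and 52. Within that interval, pIMMCs are covered, MAAEs are covered only permissively, and SAEs are not covered.

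The ascertainment gap is separate and also affects the year that is analysed: from month 6 on, no scheduled query is stated for SAEs or non-immune MAAEs, so their counts may be too low. The documents do not allow the size of any under-count to be estimated. In a descriptive study of 36 participants this calls for a wording change, not a redesign. It is worth making because these figures belong to a promised safety table.

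**What to change.** 1. In section 10.4, keep the one-year figure in the study report. Add that an addendum will give numbers and proportions of participants with SAEs, MAAEs and pIMMCs, by cohort, through the month-18 contact. The existing rule that late collection does not delay reports can stay.
2. State the time anchor (Day 1 or dose 2) for both the contacts and the analysis horizon.
3. Amend footnote 8 so that each contact asks one open question: any hospitalisation, emergency or other medical visit, or new diagnosis since the last contact. Classify the answers afterwards as SAE, MAAE or pIMMC.

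The cost is a sentence in section 10.4 and one question at calls already scheduled. The downside is a later final table and a few unrelated MAAEs to code.
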